1. SUMMARY

A pilot controlled clinical study is proposed to evaluate and compare the degree of satisfaction and skin comfort with cosmetic creams PB-011 and PB-012 in oncology patients who have developed palmar and plantar peripheral poly-neuropathy due to treatment with chemotherapy or chemotherapeutic agents fused to monoclonal antibodies (immunocytostatic). Both products are cosmetic creams derived from the line Nocisens (for the care of sensitive skin with atopic tendency). The hypothesis to be tested is that care with PB-011 or PB-012 for sensitive skin associated with palmar and plantar peripheral poly-neuropathy in oncology patients will increase their degree of satisfaction and skin comfort. A parallel, randomised, double-blind, masked, double-blind study is proposed in patients who are about to start chemotherapeutic treatment. The study involves two populations: (i) the population where PB-011 cream will be tested; and, (ii) the population that will test PB-012 cream. The duration of the project will be 12 months, and participants will have to apply the cream on their hands once a day during the period of chemotherapy treatment. A sample size of 60 volunteers per population has been estimated to ensure statistical significance. As a relevant qualitative variable for patients who have developed neuropathy, the degree of satisfaction and skin comfort will be assessed by means of a questionnaire.

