4. JUSTIFICATION AND STUDY OBJECTIVES

The toxicity generated during chemotherapy treatments can usually produce skin discomfort or peripheral polyneuropathy. CIPN manifests itself above all in the extremities, mainly in the palmar and plantar regions, giving rise to uncomfortable sensations such as itching, numbness, tingling, pain or dryness, i.e. skin sensitivity. Currently, there is no specific treatment to combat this skin sensitivity and oncology specialists recommend keeping the skin hydrated through the use of cosmetic creams.

Taking into account that these sensations imply a deterioration in the quality of life of patients, our hypothesis is that cosmetic creams for sensitive skin with references PB011 and PB012 could improve comfort and the degree of satisfaction of cancer patients with CIPN. The reason for this hypothesis is that cosmetic creams contain ingredients that reinforce the barrier function of the epidermis and improve the hydration and appearance of the skin. The study has been designed to define which of the two creams produces greater satisfaction in patients.

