5.3. Masking

To avoid bias, the study is proposed to be blind for patients and researchers and open to third parties (evaluators and those responsible for data analysis). To this end, a qualitative variable will be created, called product, of two degrees that will serve to mask the type of product used in each subject (PB-011/PB-012). The assignment of one product or another will be determined by the order of introduction in the study database. The definition of each degree of this qualitative variable will be in the possession of the main researcher and only when the study has finished and its results have been digitized, will it be transferred to those responsible for the statistical analysis. Both the data notebook and the databases or files used for statistical analysis will be dissociated from the identification data of the subjects under study.

Doctors and other study collaborators will have access to a list containing a fixed order of the products (A/B). For instance: product 1 is A, product 2 is B, product 3 is B... Investigators will assign a cream A/B to participants as they enter in the study (participant 1 will have A, 2 will have B, 3 will have B, etc). This list will be available physically and electronically.

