6. SELECTION OF SUBJECTS

The inclusion of 120 patients who have been diagnosed with cancer in stages I-III and who are going to start chemotherapy treatment is proposed. Once the treatment is finished, the degree of cutaneous comfort will be compared between the patients who have developed peripheral neuropathy in both groups.

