6.3. Expected number of subjects and justification

A total of 120 volunteers diagnosed with any type of cancer, in stages I-III, who are about to start or have received a maximum of 1 dose of chemotherapy treatment will be studied.

Two study populations are contemplated: (i) population that will receive the PB-011 cream; (ii) population that will receive the PB-012 cream. Both populations will apply the cream on their hands once a day. If sensory discomfort or, in the worst case, peripheral neuropathy appear during the chemotherapy treatment period, the application will be increased to twice daily on the affected areas (generally hands and feet).

The number of volunteers for the study is 60 for each population. This value is based on: (i) a difference of 2 points between both populations (PB-011 and PB-012), on a satisfaction scale of

0 to 10 points, with 0 being very dissatisfied and 10 very satisfied, or 2 points on the Von Frey scale; (ii) a variability (standard deviation) of 3 points in each population; (iii) a p-value of statistical significance <0.05 and, (iv) a probability of finding a statistically significant difference for the p-value <0.05 of 95%.

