8. STUDY DEVELOPMENT AND EVALUATION OF THE RESPONSE

8.1. Study variables

Main Variable: degree of skin satisfaction/comfort with the skin in the palmar and plantar regions, evaluated by means of the DLQI questionnaire.

Secondary Variables:

- Skin sensitivity quantifiable by the Von Frey filament test for patients who voluntarily so wish.
- Follow-up of discomfort skin sensations experienced by patients, evaluated by means of a brief questionnaire.

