9.1. Detection and documentation of adverse events

Adverse events can be detected either by the subject himself or by the investigator, but it is the investigator's responsibility to record them. The Data Notebook will have a section for recording adverse events (Annex V) in which the investigator, or one of his collaborators, must describe events of this type in detail. The method of detecting adverse events can be either by direct communication from the subject under study, by exploration by the investigator, or by the subject's response to a question asked by the investigator or by any collaborator of the study.

In any case, the existence of an adverse event must be duly documented and the nature of the event, the date of detection and the start date if they do not coincide, the duration, severity and possible relationship with the event must be recorded at each visit. product under study.

The subjects in whom an adverse event is detected will be subjected to additional follow-up by the researchers, who will control the evolution of the adverse events until they have disappeared, decreased or stabilized. Follow-up information for these subjects should be brought to the attention of the study monitor.

In addition to documenting the occurrence of any unexpected events, investigators should assess their intensity based on the following scale:

- Mild: adverse event that causes minimal discomfort, tolerable by the subject and that does not interfere with their daily activities.
- Moderate: An adverse event bothersome enough to interfere with normal daily activities.
- Severe: event or adverse reaction that requires hospitalization of the subject or prolongs it, that endangers his or her life, causes invalidity or permanent incapacity, gives rise to some anomaly or congenital malformation, or that produces his or her death). For notification purposes, those suspected adverse events or adverse reactions that are considered important from a medical point of view, even if they do not meet the above criteria, will also be treated as serious.

Unexpected adverse reaction: adverse event whose nature or severity does not correspond to the information in the product's technical data sheet.

9.2. . Assessment of causality

The investigator should make every effort to explain each adverse event and assess its relationship, if any, to treatment with the study product. Causality should be assessed using the following categories:

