12. STATISTICAL ANALYSES

The analysis of the results of this study will be approached from two perspectives. On the one hand, the modified intention-to-treat (MITT) population will be analyzed, which corresponds to all those subjects who have used the product at least once and for whom satisfaction data is available. On the other hand, a per-protocol analysis will be carried out in which all randomized subjects who have followed the study instructions until the end of the study will be included.

The clinical evaluation data may be analyzed as quantitative or qualitative variables. In the first case, the results will be expressed as mean \pm standard deviation, minimum and maximum. In the case of qualitative variables, the results will be expressed as frequency and percentage. For all the parameters to be measured (both clinical variables and responses to questionnaires) there will be a baseline measurement taken before the start of the protocol that will serve as a control measurement. The change in the main variable (degree of satisfaction) will be analyzed

using the paired Student's T test. The change in the secondary variables will be studied according to their nature (qualitative or quantitative variables) and applying the corresponding test in each case: Chi square, Student's T, ANOVA, Kruskal-Wallis or Mann-Whitney U. The impact of each variable on the main variable will be assessed, especially the impact of treatment, diagnosis, age and gender.

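### Section 12 tests the main variable only before versus after, so the PB-011 versus PB-012 comparison for which the trial is sized has no named test or estimate

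*Combined protocol and SAP*

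**What the plan says.** The aim is comparative. Section 4: "The study has been designed to define which of the two creams produces greater satisfaction in patients". Section 6 plans that, after chemotherapy, "the degree of cutaneous comfort will be compared between the patients who have developed peripheral neuropathy in both groups". Section 6.3 bases the sample size on "a difference of 2 points between both populations (PB-011 and PB-012", with SD 3 in each population, significance at 0.05 and 95% power, giving 60 per arm. The main variable in section 8.1 is "degree of skin satisfaction/comfort with the skin in the palmar and plantar regions, evaluated by means of the DLQI questionnaire".

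The Summary also carries a before-after hypothesis, that use of either cream "will increase their degree of satisfaction and skin comfort".

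Section 12 promises a baseline for every parameter, questionnaires included, to act as the control value. It then analyses the change in the main variable "using the paired Student's T test. The change in the secondary variables will be studied according to their nature". Chi-square, Student's t, ANOVA, Kruskal-Wallis and Mann-Whitney are listed for the secondary variables. A last sentence says that the effect of several factors on the main variable, among them treatment, will be assessed. It names no test, model, effect measure or interval.

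**The concern.** A paired t test asks whether patients changed from their own baseline. It does not ask whether one cream did better than the other. Followed as written, section 12 yields a before-after p value, pooled or per arm, and no PB-011 versus PB-012 result for the main variable. The before-after change also spans a course of chemotherapy, so it cannot be credited to a cream.

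Two risks follow. A reader may compare significance across arms and declare a winner when the creams do not differ. And because no comparison is fixed, its form could be chosen after the product code reaches the statisticians (section 5.3). The comparison matters in practice: section 2.3 says the better-accepted formulation will be the one marketed.

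**Working it through.** **Inputs (section 6.3).** Difference 2, SD 3 per arm, alpha 0.05, power 95%, 60 per arm. Sidedness is not stated. No correlation between baseline and end score is given, and no SD for the DLQI. Correlations (r) and reduced numbers below are therefore assumptions, and SD 3 is the figure for the 0-10 scale.

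**1. Reproducing the plan's number.** For two independent means, two-sided, n = 2(1.960 + 1.645)² × 3² / 2² = 58.5, so 59 per arm. The exact noncentral-t calculation gives 60 per arm (power 94.9% at 59, 95.2% at 60). A one-sided test would need only 49. The sample size is thus that of a two-sided between-arm test.

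**2. Precision of that comparison.** Half-width of the 95% CI = t(0.975, 2n − 2) × 3 × √(2/n). Fewer than 60 per arm may have end scores, because sections 7.2 and 8.2 collect them from patients who develop discomfort.

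| Analysed per arm | Power | CI half-width |
|---|---|---|
| 60 | 95.2% | 1.08 |
| 48 (assumed) | 89.8% | 1.22 |
| 36 (assumed) | 79.7% | 1.41 |
| 30 (assumed) | 71.9% | 1.55 |

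**3. The paired test is a different design.** With SD 3 at each time, SD of change = 3√(2(1 − r)). For a 2-point change at 95% power:

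| r (assumed) | SD of change | Pairs needed |
|---|---|---|
| 0 | 4.24 | 61 |
| 0.3 | 3.55 | 43 |
| 0.5 | 3.00 | 32 |
| 0.7 | 2.32 | 20 |

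These are total pairs. At r = 0, 60 pairs give 94.9%, so the number 60 alone does not settle which test was meant. The wording of section 6.3, a difference between the two populations, does.

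**4. Separate paired tests cannot stand in for the comparison.** Suppose both creams have the same true change, SD of change 3 (assumed), 60 per arm. If each arm is significant with probability p, exactly one is significant with probability 2p(1 − p).

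| Common true change | p per arm | Exactly one arm significant |
|---|---|---|
| 0.5 | 24.6% | 37.1% |
| 1.0 | 71.9% | 40.4% |
| 1.5 | 96.8% | 6.2% |

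**5. The unspecified choice matters.** Power for a 2-point between-arm difference, with ANCOVA residual SD = 3√(1 − r²):

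| r (assumed) | t test on change, 60 per arm | ANCOVA, 60 per arm | ANCOVA, 36 per arm |
|---|---|---|---|
| 0 | 72.6% | 95.2% | 79.6% |
| 0.3 | 86.5% | 96.7% | 83.2% |
| 0.5 | 95.2% | 98.7% | 89.6% |
| 0.7 | 99.7% | 99.9% | 97.4% |

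A t test on end scores alone has 95.2% at 60 per arm whatever r is.

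**6. Is there a baseline?** Section 12 promises one. Sections 7.2 and 8.2 place the questionnaires at the end of chemotherapy for patients with discomfort; section 3 says fortnightly. None of these schedules a baseline questionnaire, but none rules it out, and the data notebook is not shown. The choice between ANCOVA and a t test on end scores depends on the answer.

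**The case against.** The strongest reply is that the comparison is under-described, not missing. Section 12 does say that the effect of treatment on the main variable will be assessed. Section 5.3 says that "a qualitative variable will be created, called product, of two degrees that will serve to mask the type of product used in each subject", and section 9.2 speaks of "treatment with the study product", so treatment probably means the cream, although elsewhere the word often means chemotherapy. The study calls itself a pilot, and the paired test does fit the hypothesis in the Summary. All of this is fair and shows intent. None of it supplies a test, model or estimate, and the pilot label does not remove a comparison that the trial states as its aim and powers at 95%.

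Four further points stand as limits on the remedy:

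- **Instrument.** The sample size uses a 0-10 satisfaction scale, while the main variable is the DLQI. If satisfaction with the cream (Annex IV, item 3) were meant, no baseline could exist and ANCOVA would not apply.
- **Analysis set.** Section 12 does not say whether the modified intention-to-treat or the per-protocol set is primary.
- **Blinding of analysts.** Section 5.3 calls the study open to those analysing the data, yet withholds the code from them until results are digitised. Release of the code may not be a safe cut-off.
- **Subset.** End scores restricted to patients with discomfort define a group after randomisation, which a between-arm test does not cure.

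**Conclusion.** The concern holds and needs correction before analysis. The only test named for the main variable cannot answer the question the trial states and is sized for, and the sentence on the effect of treatment does not fill the gap. The sample size arithmetic is sound for a two-sided two-sample t test: 95.2% power and a half-width of 1.08 points, provided the outcome is on the 0-10 scale with SD 3 and 60 per arm are analysed. The risk of a spurious winner from separate paired tests is 6% to 40% over the common changes examined, assuming SD of change 3. Confidence is high that the gap exists; which between-arm model suits depends on whether the baseline is taken and which instrument is scored.

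**What to change.** In section 12:

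- Make the primary analysis of the main variable a between-arm comparison, reported as the PB-011 minus PB-012 difference with 95% CI.
- If the promised baseline DLQI is collected, use ANCOVA of the end-of-chemotherapy DLQI adjusted for baseline. Otherwise use a two-sample t test on the end-of-chemotherapy score.
- Fix which applies, and which analysis set is primary, before anyone analysing the data can see product assignment.
- Keep the paired within-arm changes as descriptive results for the Summary's hypothesis.

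In sections 7.2 and 8.2, state when the baseline questionnaires are taken, and reconcile the fortnightly schedule in section 3 with end-of-chemotherapy collection.

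The cost is wording in section 12 and one line in the schedule. If no baseline questionnaire is now taken, ANCOVA adds one short set at inclusion, already promised by section 12. Naming the test does not itself change the planned 120. Whether 60 per arm is enough still depends on two separate matters: the mismatch between the DLQI and the sizing scale, and the restriction of end scores to patients with discomfort.

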3. INTRODUCCIÓN

The impact of cancer in the western world and the growing number of people affected each year¹ means that new, increasingly effective and selective treatments are appearing relatively quickly. However, although these treatments are highly effective in killing tumour cells, they are not their only target. Molecules used in cancer treatments often affect healthy cells, causing side effects (nausea, diarrhoea, anaemia, immunosuppression, fatigue and hair loss). When antineoplastic therapies affect the sensory peripheral nervous system, they can cause peripheral polyneuropathy (NP or CIPN (Chemotherapy-Induced Peripheral Neuropathy)). The prevalence of this disease varies depending on the chemotherapy agent administered, affecting up to 80% of patients treated with taxanes (paclitaxel and/or docetaxel) or up to 95% of patients treated with oxyplatin². People with PN experience sensory discomfort, mainly in the extremities (numbness, dryness, tingling, burning, stinging, allodynia or hyperalgesia)³ which, over time, can

lead to the interruption of cancer treatment, with the risks that this entails. This condition often persists after the end of cancer treatment, which greatly affects the quality of life of those who suffer from it, as it can be uncomfortable when working, playing sports, carrying out household chores and even when socialising. In addition, the uncomfortable sensations can disturb sleep, which has an impact on mood. In general, people with NP caused by cancer treatments feel a great dissatisfaction with their skin.

Currently, there is no effective treatment for NP, and when the symptomatology is severe and limits patients' daily life, some doctors recommend taking antidepressants, such as duloxetine, or discontinuing chemotherapy treatment⁴. Although a number of clinical trials aimed at finding an effective treatment for NP have been conducted in recent years, none of them have proven to be effective. Therefore, understanding the mechanisms governing the development of PN and its treatment is a huge challenge in oncology as it is one of the main causes of chemotherapy withdrawal.

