6.1. Inclusion criteria

Patients must meet all the criteria that appear in this section to be included in the study.

- To be older than 18 years old.
- To be able to complete questionnaires.
- Give informed consent in writing.
- Being able to apply the product under test by oneself.
- To have been diagnosed with stage I-III primary cancer.
- To have received a maximum of one treatment session with chemotherapy (derivatives of taxane, platinum or vincristines).
- Eastern Cooperative Oncology Group (ECOG) performance status (PS) 0-2.
- Life expectancy greater than or equal to 6 months.

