8.2. Collection of variables

The main variable, degree of skin satisfaction/comfort, will be evaluated using the DLQI^{12, 13} questionnaire available in ANNEX II.

Mechanical sensitivity will be assessed by means of the Von Frey filament test in patients who voluntarily want to undergo it. The pain threshold and mechanical allodynia of patients with post-chemotherapy polyneuropathy will be measured before starting the study and once the chemotherapy treatment is over, expressing the threshold in the minimum number of pressure units that trigger pain in patients with the corresponding filament. of Von Frey approved.

The follow-up of the patients will be carried out through the usual oncological control during treatment. If the patients develop sensory or skin discomfort during this period, at the end of the treatment a check-up will be carried out using the following questionnaires:

- Follow-up of discomfort sensations available in a questionnaire derived from the Leonard Scale (ANNEX III).
- Degree of skin satisfaction by means of the Dermatology Life Quality Index [DLQI] (Annex II).
- Degree of satisfaction with the cream (Annex IV).

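### The sentence on influences on the main variable sets no limit to entry factors and uses *treatment* ambiguously, so section 12 specifies no clean between-cream model

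*Combined protocol and SAP*

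**What the plan says.** Section 12 names one test for the main variable, a paired t-test of change. It closes with: "The impact of each variable on the main variable will be assessed, especially the impact of treatment, diagnosis, age and gender". No model form, covariate list or timing limit follows.

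Section 8.1 defines the main variable as "degree of skin satisfaction/comfort with the skin in the palmar and plantar regions, evaluated by means of the DLQI questionnaire". The only other study variables it lists are two outcomes: "Skin sensitivity quantifiable by the Von Frey filament test for patients who voluntarily so wish" and "Follow-up of discomfort skin sensations experienced by patients, evaluated by means of a brief questionnaire". Under section 8.2 the Von Frey thresholds "will be measured before starting the study and once the chemotherapy treatment is over". The discomfort, DLQI and cream-satisfaction questionnaires are given at the end of chemotherapy to patients who develop discomfort. Section 12 also promises a baseline measurement of every parameter, but does not say that the baseline is the value used when influences are assessed.

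On chemotherapy, section 3 says "The prevalence of this disease varies depending on the chemotherapy agent administered", with rates of up to 80% for taxanes and up to 95% for the platinum agent it names. Section 6.1 admits taxane, platinum and vincristine derivatives, and one entry condition is "To have received a maximum of one treatment session with chemotherapy", so patients enter after 0 or 1 session. Section 6.3 plans for "A total of 120 volunteers diagnosed with any type of cancer". Section 5.2 specifies simple randomisation, with no stratification.

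**The concern.** Section 4 says the study is meant to show which cream satisfies patients more. A paired t-test compares each patient with himself or herself and does not compare the creams. The closing sentence of section 12 is therefore the only place in that section where a cream effect on the main variable could be estimated, and its wording leaves two things open.

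First, *each variable*, read alongside section 8.1, can take in end-of-treatment discomfort and Von Frey values. These are outcomes the cream may change. Putting them in a model beside cream changes the question from the effect of the cream to the part of that effect not passing through those outcomes.

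Second, *treatment* has two meanings in the document. It is chemotherapy in sections 6.4 and 8.2, and use of the study product in section 9.2. If it means the cream in section 12, the chemotherapy agent is not among the highlighted factors. If it means chemotherapy, the cream is not. Diagnosis is undefined and most naturally means the cancer. With any cancer type eligible, it is an imperfect stand-in for the agent.

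At stake are the interpretation of the between-cream estimate and the freedom to choose covariates after the codes are released.

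**Working it through.** **1. The plan's own figure.** Inputs from section 6.3: difference 2, SD 3, significance level 0.05, power 95%. Two-sided normal approximation: n = 2 × (1.960 + 1.645)² × 3² / 2² = 58.5, so 59 per arm. A two-sample t-test gives 59.45, so 60. The stated 60 per arm reproduces, and the point here does not change it.

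**2. Which variables can enter, and when they are measured.**

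| Variable | Known at entry? |
|---|---|
| Diagnosis, age, gender | Yes |
| Chemotherapy agent class, sessions before entry | Yes, but not named unless *treatment* means chemotherapy |
| Baseline DLQI | Yes, if taken as section 12 promises |
| Von Frey, before the study | Yes, in volunteers only |
| Von Frey, after chemotherapy | No, after the cream |
| Discomfort questionnaire, end of chemotherapy | No, after the cream |

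The sentence in section 12 does not separate these rows.

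**3. Illustration of adjusting for a post-cream score.** Assumptions not in the documents: total cream effect 2, SD 3, within-arm correlation 0.6 between the post-cream score and the main variable, 60 per arm. The adjusted estimate is (1 − share mediated) × 2. The residual SD after adjustment is 3 × √(1 − 0.6²) = 2.4. Simulated power over 4,000 trials per row:

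| Share of effect through the score | Adjusted estimate | Power with the score in the model |
|---|---|---|
| 0% | 2.0 | 99.6% |
| 25% | 1.5 | 91% |
| 50% | 1.0 | 58% |
| 75% | 0.5 | 18% |
| 100% | 0.0 | 5% |

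Without the score in the model, the estimate stays at about 2.0 and power at 95–96%. The power column depends on the assumed correlation. The 2 points and SD of 3 belong to the 0–10 satisfaction scale (or Von Frey) in section 6.3, not to the DLQI. The table shows direction and mechanism and is not a forecast for this trial.

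**4. Chance imbalance in the agent.** Treat the number on a given agent in each arm as binomial(60, p). A gap of 10 percentage points is 6 patients. For p = 0.5 (assumed), the SD of the difference in counts is √(2 × 60 × 0.25) = 5.48, and P(|difference| ≥ 6) = 32%. For p = 0.3 (assumed) it is 27%. For a gap of 15 points (9 patients) the values are 12% and 9%.

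**5. What such an imbalance could do.** Taking section 3's two upper rates at face value, a 10-point gap between the taxane and platinum shares shifts expected neuropathy incidence by 0.10 × (95 − 80) = 1.5 percentage points. That concerns who develops neuropathy. The documents give nothing from which to compute a shift in DLQI.

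**The case against.** The strongest reply is that the plan never says the cream effect will be adjusted for anything. Assessing the impact of each variable may mean one-at-a-time associations, which bias no cream estimate. A baseline-only reading is also possible, since baselines are promised. This stands: the bias is conditional on post-cream values entering a joint model with cream. A reader might infer that the plan commits to such a model; the text does not support that. It leaves the choice open.

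A reader might also infer that the agent is excluded. It is not. *Especially* introduces a list of emphases, and *each variable* could cover the agent if it is recorded. What can be said is that the agent or the cream is not highlighted, depending on what *treatment* means.

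A third tempting step is to call the agent the strongest predictor available. Section 3 links it to the prevalence of neuropathy. Section 6 compares comfort among patients who have developed neuropathy, and no section says the agent predicts DLQI within that group. Baseline DLQI is a more direct candidate.

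Finally, the analysis changes no sample size, and any statement of power lost or patients saved rests on assumed correlations and on a scale that is not the main variable. That also stands. It limits how large the problem can be said to be, but it does not settle the wording.

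**Conclusion.** The point holds as a defect of specification. Section 12 allows post-cream outcomes among the influences on the main variable, uses a word with two meanings for a key factor, and names no between-cream model for the main variable. If post-cream values are modelled jointly with cream, the estimate can be biased, usually toward zero when the effect runs through them. If they are examined singly, the results are descriptive only.

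The size cannot be derived from the documents. The attenuation from 2 points to 1 is an illustration with half the effect mediated. The 32% chance of a 10-point imbalance is an illustration with an assumed 50% agent share and 60 per arm, and its effect on DLQI is unknown. The change is worth making because it is cheap and settles the model before the product codes are released.

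**What to change.** Replace the sentence in section 12 with one pre-specified between-cream model for the main variable:

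- Outcome: end-of-treatment DLQI.
- Terms: cream, baseline DLQI, chemotherapy agent class, sessions before entry (0 or 1), age and gender. Keep diagnosis if numbers allow.
- Make this the cream comparison, and keep the paired t-test as a within-arm description only.
- State that secondary variables and any other post-assignment measure are not covariates for the cream effect, and that their associations with the main variable are exploratory.
- Write *cream* and *chemotherapy* in place of *treatment*.

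Cost: no extra patients or visits. The model spends a few degrees of freedom, which matters more if the neuropathy subset of section 6 turns out small. Section 12 is protocol text, so section 11.4 requires documented agreement of the parties, and ethics committee review may be needed. The data notebook (Annex I) is a separate attachment, so check that it records agent class, prior sessions and baseline DLQI.
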